4.4 Interim Analyses and Data Monitoring

It is planned to produce two formal statistical summaries. The first will be when all patients enrolled in the long-term extension at LPFT of the PATENT-1 study have reached Visit 5 and the PATENT-1 study has been unblinded. The second will be at the conclusion of this extension study. Additional summaries will be performed, at least on a yearly basis, to monitor long-term safety.

4.5 Data Rules

Efficacy analysis datasets will be created that include key demographic data that will be used for the descriptive subgroup analyses. These datasets will also include results from the imputations of missing values in the period up to week 12 and end of study, such that the descriptive efficacy analyses can be performed without the need for major pre-processing within the statistical analysis programs.

4.6 Blind Review

All subjects receiving treatment in the long-term extension will be valid for the descriptive safety and efficacy analyses. Hence, there will be no formal validity assignment.

5. Analysis Sets

The safety and efficacy analyses will be performed in subjects entering and treated in the long-term extension. Formally, these can be considered the long-term safety population.

A subject is valid for the long-term safety and efficacy analysis, if at least one dose of study medication in the extension period was administered.

5.1 Assignment of analysis sets

A subject is valid for the long-term safety and efficacy analysis, if at least one dose of study medication in the extension period was administered.

6. Statistical Methodology

The statistical evaluation will be performed according to the company Global Standards for demography and safety analyses when these have been published (see section 1 for table templates), the statistical methods given in the protocol and, if applicable, any relevant protocol amendments.

For all descriptive analyses, unless otherwise specified, it is planned to summarize the group of subjects as a whole ("all subjects") and by the following groups:

Reference Number: RD-OI-0119

Supplement Version: 8

- Patients randomized to riociguat individual titration in the main phase who stayed on riociguat in the LTE phase, referred to as "riociguat individual titration"
- Patients randomized to placebo in the main phase who switched to riociguat in the LTE phase, referred to as "placebo-riociguat"

By week 8 of the extension, all subjects should be receiving riociguat at the optimized dose, but prior to this there may be some differences between the treatment groups as those subjects in the placebo group will be receiving active medication for the first time, or those in the 1.5 mg group will be up-titrated above 1.5 mg for the first time.

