#### Titration Phase (8 weeks):

##### General aspects:

During the first eight weeks of the trial, patients from the Placebo Arm and from the BAY 63-2521 1.5 mg Dose Arm (applies only to patients who reached the 1.5 mg tid level) of PATENT-1 trial will be up-titrated, if tolerated, up to 2.5 mg BAY 63-2521 tid according to an individual dose titration scheme.

To maintain the blinding of PATENT-1, the PATENT-2 study medication (BAY 63-2521) is blinded with respect to the dose during the Titration Phase and investigators will not know at which dose level a certain patient enters the PATENT-2 trial.

Patients from the BAY 63-2521 Individual Dose Titration Arm and the BAY 63-2521 1.5 mg Dose Arm will enter the extension trial on the same dose level

which they have received on the last day of PATENT-1, while patients from the Placebo Arm will start at Visit 1 with a BAY 63-2521 dose of 1.0 mg tid.

To allow a blinded individual dose titration, the titration will be performed with the aid of an IVR-System. At each Titration Visit (with the exception of Visit 1) the investigator needs to decide, based on the patient's systolic blood pressure, if the study medication dose should be modified. The respective decision (increase, maintain or decrease dose) must be entered in the IVR-System that will automatically allocate the right dose in accordance with the respective titration scheme. Afterwards, the investigator will be informed by the system, which of the blinded medication bottles (blinded with respect to the dose) needs to be handed over for the next titration period (starts always with the morning dose).

Independently from the patient's allocation to a specific treatment arm in PATENT-1, the investigators will apply the following blood pressure based titration rules for their dose decision in PATENT-2:

The individual study medication dose of the next titration step will be determined every 2 weeks according to the peripheral SBP measured at trough before intake of the morning dose under consideration of the following algorithm (= individual dose titration scheme):

- If trough SBP  $\geq 95$  mmHg, increase dose (+0.5 mg tid).
- If trough SBP 90 - 94 mmHg, maintain dose.
- If trough SBP  $< 90$  mmHg without symptoms of hypotension, reduce dose (-0.5 mg tid).
- If any SBP  $< 90$  mmHg with clinical symptoms of hypotension such as dizziness or presyncope, stop study treatment; restart after 24 hours with reduced dose (-0.5 mg tid).

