**Main-Study Phase (Duration until BAY 63-2521 receives official approval and will be commercially available):**

From Visit 5 on (begin of the Main-Study Phase) investigators are allowed to modify the BAY 63-2521 dose in a dose range between 0.5 mg tid and 2.5 mg tid according to the patient's need. In contrast to the Titration Phase, patients may be up-titrated between regular scheduled visits. In this context, investigators have to consider the patient's blood pressure (refer to the individual dose titration scheme), potential BAY 63-2521 side effects and the progression of the underlying Pulmonary Hypertension.

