### **Laboratory Parameters**

All blood samples will be analyzed in a central laboratory until V6.

Laboratory procedures will be described in a separate laboratory manual.

At the latest at the end of the study when all planned analyses are completed, all blood samples will be destroyed.

- ***Hematology, clinical chemistry, coagulation test***

Hematology (white blood cell differential count, erythrocytes, hemoglobin, hematocrit, platelets)

Coagulation tests (PTT, INR)

Clinical chemistry (AST, ALT, ALP, GGT, GLDH, CK, lipase, CHE, creatinine, urea, uric acid, total bilirubin, total protein, serum albumin, sodium, potassium, calcium, phosphate)

Note: Calcium and phosphate will only be analyzed for patients who were included under amendment 8 of study 12934.

Frequency: At every visit until V6 (except Visit 1)

- ***NT-proBNP***

Frequency: At every visit until V6 with the exception of Visit 1 and Safety Follow Up Visit

Changes from baseline NT-proBNP will be considered as a secondary efficacy endpoint in PATENT-1. To ensure the blinding of the treatment regime of PATENT-1, the results of the NT-pro BNP determinations at PATENT -2 Visits 2-5 will not be forwarded to the investigators before lock of the PATENT-1 database. In contrast to that the results of the NT-pro BNP determination at PATENT-2, Visit 6 will be forwarded to the investigators.

- ***Pregnancy testing***

Methodology: Determination of  $\beta$ - human chorionic gonadotropin in blood serum or urine

Frequency: Will be performed centrally at Visit 6 and locally at least at every Main-Study Phase Visit (V7-Vn) and at Safety Follow Up Visit. Based on country specific regulations further measurements might be performed.

In addition to the above mentioned serum  $\beta$ - human chorionic gonadotropin tests, a urine test will be performed at Visit 6 of PATENT-1 study if the patient will

participate in the extension study. Female patients with childbearing potential can be enrolled into the extension study based on the result of this test.

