## **6. STATISTICAL METHODS AND DETERMINATION OF SAMPLE SIZE**

### **6.1 Statistical and Analytical Plans**

The aim of this long-term extension study is primarily the assessment of safety and tolerability, so no single primary variable has been identified. Patient numbers will be determined by those completing the PATENT-1 study and willing to enter the PATENT-2 study. As the extension is of an open label design with no comparator group, all statistical analyses will be descriptive. The summary tables will be presented for the overall group of patients, and also split by previous treatment groups in PATENT-1. Baseline will be week 0 in PATENT-1 (changed with amendment 11).

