All subjects entering the extension study first participated in a blinded 8-week titration phase. The dose of riociguat was increased, maintained, or decreased depending on whether peripheral systolic blood pressure (SBP) was ≥ 95 mmHg, 90 – 94 mmHg, or < 90 mmHg, in accordance with the following rules:

- Subjects from the former placebo group of the PATENT-1 study started at Visit 1 with a riociguat dose of 1.0 mg tid. The individual riociguat dose was up-titrated in steps of 0.5 mg tid every 2 weeks up to a maximum of 2.5 mg tid.
- Subjects from the former riociguat 1.0–1.5 mg tid capped dose titration group of PATENT-1 entered the extension trial on the same dose level as they received on the last day of PATENT-1. Subjects whose last dose in PATENT-1 was 1.0–1.5 mg tid were up-titrated in steps of 0.5 mg tid every 2 weeks up to a maximum of 2.5 mg tid. Subjects whose last dose in PATENT-1 was 1.0 mg or 0.5 mg tid underwent sham titration, with no increase in dose of study drug before the end of the titration phase.
(titration approach modified by protocol amendment 5)
- Subjects from the former riociguat 1.0-2.5 mg tid group of PATENT-1 entered the extension trial on the same dose level as they received on the last day of PATENT-1. Subjects underwent sham titration, with no increase in dose of study drug before the end of the titration phase.

Reference Number: RD-OI-0119

Supplement Version: 8

During the main study phase, investigators (unblinded to dose) could modify the riociguat dose in a range between 0.5 mg tid and 2.5 mg tid according to the subject's need.

Dose reductions for safety reasons were allowed at any time.

For further details see integrated study protocol, amendment 11, version 1.0, Section 4.1.

4. General Statistical Considerations

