6.4 Safety

Safety variables are:

- Adverse events
- Mortality
- Laboratory parameters
- Vital signs
- ECG parameters
- Blood gas analysis

Baseline for continuous safety variables will be week 0 of study 12934.

The incidence of treatment-emergent adverse events during the extension will be tabulated by treatment group. Adverse events are considered to be treatment-emergent if they have started or worsened after first application of study medication up to 2 days after end of treatment with study medication. Further tables will be produced for serious and/or drug-related treatment-emergent adverse events. The incidence of adverse events during follow-up (that is, adverse events occurring more than 2 days after end of treatment with study medication) will be

tabulated separately. The incidence of adverse events that started in the main study 12934 and continue into study 12935 will also be tabulated separately.

In addition, given the varying length of time subjects are in the long-term study, the incidence of treatment-emergent adverse events will also be give per 100 subject years.

Mortality will be summarized descriptively. Any deaths in the study period will be listed, with day of death relative to start and stop of study drug and cause of death.

The safety evaluation of laboratory data will include

- listings of laboratory data out of normal range
- incidence rates of treatment-emergent laboratory values outside of normal range by treatment group
- incidence rates of pre-specified laboratory data abnormalities by treatment group
- descriptive analysis of continuous laboratory parameters, and their changes from baseline by visit and treatment group

The specific laboratory data abnormalities are consistent with those requested by the Data Monitoring Committee or as part of the company medical safety review, and include hepatic transaminases, bilirubin and creatinine (and calculated eGFR).

With global amendment 11, a laboratory value testing was completely removed from the study protocol.

Vital signs (systolic BP, diastolic BP, heart rate and weight) and blood gas analysis will be summarised by visit and treatment group for the population of subjects valid for safety.

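### SAP 6 gives the former PATENT-1 riociguat 1.5 mg arm no column in the default tables, although protocol 6.1 requires a split by previous treatment group

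*SAP*

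**What the plan says.** Protocol 6.1 sets the table layout: "The summary tables will be presented for the overall group of patients, and also split by previous treatment groups in PATENT-1". Protocol 4.1 and SAP 3 each describe three PATENT-1 arms entering the extension: placebo, individual dose titration up to 2.5 mg tid, and riociguat capped at 1.5 mg tid.

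The opening text of SAP 6 sets a default for all descriptive analyses unless something else is specified: all subjects, plus two groups. The first is "Patients randomized to riociguat individual titration in the main phase who stayed on riociguat in the LTE phase"; the second is the placebo patients who switched to riociguat. The list ends there. The next paragraph expects differences between the groups before week 8, partly because "those in the 1.5 mg group will be up-titrated above 1.5 mg for the first time".

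In SAP 6.4 the basic safety table is specified as follows: "The incidence of treatment-emergent adverse events during the extension will be tabulated by treatment group". The laboratory, vital-sign, blood-gas and ECG summaries use the same term, and the section never says which groups it means. SAP 6.2 lists many subgroups but no former arms. The PK boxplots in SAP 6.3 do name all three former arms. SAP 6.1 speaks of former treatment groups for demographics, and of the former 1.5 mg and placebo groups for dose titration.

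**The concern.** The SAP departs from a layout rule in the protocol and gives no reason. SAP 7 describes version 5.0 only as a move to a new template. The departure falls on the safety tables, and safety is the main purpose of the study.

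The omitted arm is also informative. In the individual-titration arm, "Subjects underwent sham titration, with no increase in dose of study drug before the end of the titration phase". Placebo patients start active drug for the first time. Only the 1.5 mg arm contains patients who are already treated and then go above their PATENT-1 dose under blinded conditions. Protocol 4.5.4 reports a clear rise in adverse events at 2.5 mg tid in healthy volunteers, so a reader would want to see this step separately. With the two-group default it is mixed into the total.

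**Working it through.** No sample size, power or event figure is involved, so the check is a comparison of the texts and some counts.

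**Groups required and groups shown**

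| Former PATENT-1 arm | Enters PATENT-2 (protocol 4.1, SAP 3) | Default column (SAP 6) | PK boxplots (SAP 6.3) |
|---|---|---|---|
| Individual dose titration | yes | yes | yes |
| Placebo | yes | yes | yes |
| Riociguat 1.5 mg capped | yes | **no** | yes |

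Protocol 6.1 implies 3 arms + 1 total = 4 columns. SAP 6 gives 2 + 1 = 3.

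**Which outputs inherit the default.** The SAP 6.4 summaries by treatment group, or by visit and treatment group, are:

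1. treatment-emergent adverse events
2. laboratory values outside the normal range
3. pre-specified laboratory abnormalities
4. continuous laboratory parameters
5. vital signs and blood gases
6. ECG abnormalities
7. continuous ECG parameters

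That is seven summaries, none with its own definition of the groups. The default therefore applies to 7 of 7. It also applies to the efficacy tables in SAP 6.2, including 6MWD, WHO class and clinical worsening. The PK boxplots are an explicit exception. Demographics and dose titration in SAP 6.1 are arguable ones.

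**Size of the dose step.** Protocol 4.1 limits true up-titration in this arm to patients who reached 1.5 mg tid, in 0.5 mg steps, with increases possible at Visits 2, 3 and 4.

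- Visit 2 (day 14): 1.5 + 0.5 = 2.0 mg tid
- Visit 3 (day 28): 2.0 + 0.5 = 2.5 mg tid
- Relative rise: (2.5 − 1.5) / 1.5 = 67%

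This is the largest possible dose change. It does not measure the effect of leaving out the column.

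**How much by-visit data falls in the window.** Under the current flow chart the Titration Phase ends at Visit 5 (day 56).

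- Laboratory: Visits 2–6 are scheduled, of which Visits 2–5 fall in the phase: 4/5 = 80%
- ECG: Visits 1–6 are scheduled, of which Visits 1–5 fall in the phase: 5/6 = 83%

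The schedule was cut back by Amendment 11 in December 2012. Laboratory and ECG data collected after Visit 6 under earlier versions probably exist and would lower both shares.

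**Limit of the dose argument.** From Visit 5, "investigators are allowed to modify the BAY 63-2521 dose in a dose range between 0.5 mg tid and 2.5 mg tid", whichever arm the patient came from. The contrast in dosing rules is therefore confined to the first 8 weeks. The missing column affects the whole extension.

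**The case against.** The strongest reply is that SAP 6.4 can be read with three groups. The paragraph after the two-group list counts the 1.5 mg patients among the treatment groups, SAP 6.3 lists three, and SAP 6 says it follows the protocol's methods. On that reading the columns are ambiguous rather than missing. The table specifications are also in a separate document that is not available here. This shows that the SAP is inconsistent with itself, but it does not displace the rule. SAP 6 says what applies when nothing else is specified, and SAP 6.4 specifies nothing else. Table shells with three columns would contradict the SAP.

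A bullet might have been lost in the text extraction, since a page header precedes the list. Nothing in the text points to that.

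The first formal summary, planned for when the specified patients have reached Visit 5, may already have shown the titration window by arm. That is possible, but it would not replace the final tables.

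All analyses are descriptive, and SAP 4.6 keeps every treated patient in. This is true and limits the seriousness. Counts for the omitted arm could be recovered by subtraction. The medians and quartiles that SAP 4.1 requires could not, nor could an arm-specific Kaplan-Meier curve for clinical worsening.

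Two further points stand. The 80% and 83% shares depend on the current schedule and are secondary. A third column would also mix up-titrated with sham-titrated patients, and adverse events are tabulated over the whole extension, so the column alone does not isolate the dose step.

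**Conclusion.** The concern holds. As written, SAP 6 drops one of the three former arms from the default efficacy and safety tables, against protocol 6.1 and without explanation. The gap covers all seven by-group summaries in SAP 6.4. It is a reporting gap: the patients stay in the analysis set and in the total. It should be fixed, because it affects the core safety tables and hides the only previously treated patients whose dose could rise during the Titration Phase.

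The conclusion assumes that the two-group list is complete as printed and that the default means what it says. The dose argument uses the protocol's restriction to patients who reached 1.5 mg tid. SAP 3 places a last dose of 1.0 mg tid under both true and sham up-titration, and the two texts must be reconciled. The documents give no arm sizes, so the proportion of patients affected cannot be stated.

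**What to change.** Add a third default group to SAP 6: patients randomized in PATENT-1 to the riociguat 1.5 mg capped arm who continued on riociguat in the extension. Use the same three labels plus the total in SAP 6.1, 6.2, 6.3 and 6.4, and replace the undefined term in SAP 6.4 with a reference to them. Because the arm mixes patients with true and sham up-titration, footnote the number who entered the extension at 1.5 mg tid.

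The change costs one bullet, one table column and one footnote, all from data already collected. The only drawback is wider tables. If the sponsor keeps two groups on purpose, SAP 7 must record and justify this as a change from protocol 6.1. That would explain the gap but not close it.

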6.1 Population characteristics

Demographic variables and baseline characteristics will be summarized by former treatment group for the long-term safety population.

New ("treatment-emergent") and current concomitant medication received during the long-term extension will be summarized, coded by ATC codes (WHO-DD).

Specific concomitant medications will also be summarized by class and corrected generic name:

1. PH specific medication (note, for the PAH indication PDE5Is are excluded entirely until after stop of riociguat):

- ERAs (bosentan, ambrisentan, sitaxsentan)
- Prostacycline (iloprost, epoprostenol, treprostinil)
- PDE5I (sildenafil, vardenafil, tadalafil)

2. Background therapy

- CCB
- diuretics
- digoxin
- oral anticoagulation
- oxygen

3. Safety relevant medication

- PPI (omeprazol, pantoprazol, rabeprazol, esomeprazol, etc)
- antacids (e.g. aluminum hydroxide, magnesium hydroxide)
- strong CYP3A4 inhibitors
- CYP3A4 inductors
- vasodilative drugs (e.g. antihypertensive medication)

Duration of study medication (in days), in total and by dose, will be summarized descriptively and by three-monthly intervals using frequency counts. Compliance (taken as a percentage of planned), over the first 12 weeks of the study and for the first four weeks after the titration,

will be summarized descriptively and in 10% intervals. Dose titration by visit, dose titration sequence and reasons for up- and down-titration by visit and dose (after titration) will also be summarized using frequency counts. Formally, the dose titration information should just be needed for the former riociguat 1.5 mg and placebo groups, but as the investigators and subjects remain fully blinded during the 8 week (sham) titration phase, in theory those subjects randomized to the riociguat Individual Dose Titration group, despite actually being on a stable dose of study medication, could also have a sham dose adjustment.

6.2 Efficacy

Efficacy variables are:

- 6 minute walking distance from the 6MWT
- PVR (no RHC required at any time during study, PVR only measured if RHC performed as part of regular diagnostic work up)
- NT pro-BNP
- WHO functional class
- Time to clinical worsening
- Borg CR 10 Scale[®]
- EQ-5D questionnaire
- LPH questionnaire

In the efficacy analyses, countries and centres will be clustered by geographic region, consistent with the pooling in study 12934.

All analyses will be descriptive. For non-categorical data, absolute values and changes from baseline will be summarized. Baseline will be week 0 of study 12934.

It is envisaged that WHO functional class will either remain the same, improve by one or two categories, or deteriorate by one category in most cases. A change score (end of study minus baseline) will be calculated, which could go from -3 (class IV at baseline and class I at end of study) to +4 (class I at baseline, death at end of study), but in practice for those patients still alive at the end of the study it will most likely range from -2 to +1

Time to clinical worsening is made up of several components:

- 1) all-cause mortality
 - 2) heart/lung transplantation
 - 3) Atrial septostomy (AS)
 - 4) hospitalization due to persistent worsening of pulmonary hypertension
 - 5) start of new PH-specific treatment
 - 6) persistent decrease in 6MWD
 - 7) persistent worsening of functional class
- as defined in the protocol section 4.6.4.

The occurrence of the event of clinical worsening during the long-term extension will be summarized using categorical methods, but as an additional summary, the time to event will also be described. In determining whether an event is considered to be an event of clinical worsening the same rules as in study 12934 will be applied.

Change in the Borg CR 10 Scale[®] will be summarized using frequency counts.

The exploratory efficacy variables described in the Supplementary SAP of study 12934 will be summarized descriptively. This includes the subscales of the EQ5D and LPH and the additional haemodynamic variables. Also the sensitivity analysis of clinical worsening and the categorical analyses described in the Supplementary SAP of study 12934 will be performed.

The primary and secondary efficacy variables, except PVR, will be summarized descriptively for the following subgroups:

- therapy-naïve
- pre-treated
- pre-treated with Endothelin Receptor Antagonist
- pre-treated with Prostacyclin Analogue
- region
- idiopathic/familial PAH
- connective tissue disease
- associated (other forms) PAH
- WHO FC I/II at baseline
- WHO FC III/IV at baseline
- therapy-naïve and WHO FC I/II at baseline
- therapy-naïve and WHO FC III/IV at baseline
- pre-treated and WHO FC I/II at baseline
- pre-treated and WHO FC III/IV at baseline
- < 320m 6MWD at baseline
- ≥ 320m 6MWD at baseline
- < 380m 6MWD at baseline
- ≥ 380m 6MWD at baseline
- males
- females
- age < 65 years

- age \geq 65 years
- race.

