### **Statistical analyses of other variables**

Patients will be included in these analyses if they are included in the safety analysis and have both baseline and post-baseline data available for the variable being analyzed. For Time To Clinical Worsening, incidence tables of the overall rate and the particular event leading to clinical worsening will be presented, together with the Kaplan-Meier survival curve. Change in Borg CR 10 Scale or Modified Borg Dyspnoea Scale and functional class at each visit will be summarized by frequency counts. Patients with data on the Borg CR10 Scale and patients with data on the Modified Borg Dyspnoea Scale will be combined in the statistical analysis. Change in 6MWD, NT pro-BNP, EQ-5D and LPH at each visit will be summarized using descriptive methods.

The study endpoints related to health care resource utilization will be summarized using appropriate statistical methods: categorical variables by frequency tables and continuous variables by sample statistics. It is envisaged that all endpoints will be measured either on a semi-continuous scale or have ordered categories, and so exploratory statistical tests will be ANCOVA or the stratified Wilcoxon test, depending on the distribution.

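### Unequal follow-up is allowed for in adverse events but not in death or clinical worsening: death has no survival estimate or person-time rate, and clinical worsening has no fixed-time estimates, censoring rule or exposure-adjusted rate

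*SAP*

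**What the plan says.** **Clinical worsening.** SAP 6.2 lists seven components and states that occurrence during the extension "will be summarized using categorical methods, but as an additional summary, the time to event will also be described". It names no estimator, time points, confidence intervals or censoring rule. Protocol 6.1, on the other variables, puts the incidence tables and the curve side by side: the overall rate and "the particular event leading to clinical worsening will be presented, together with the Kaplan-Meier survival curve". The opening of SAP section 6 says the evaluation follows, among other things, "the statistical methods given in the protocol and, if applicable, any relevant protocol amendments".

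**Death.** SAP 6.4 says "Mortality will be summarized descriptively" and adds a listing with day of death relative to start and stop of study drug, and cause. Neither document names a survival estimate or a person-time rate for all-cause death.

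**Adverse events.** SAP 6.4 adds rates per 100 subject-years for treatment-emergent adverse events, "given the varying length of time subjects are in the long-term study". Treatment-emergent there means up to 2 days after the end of treatment.

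**Setting.** Protocol 6.1 states that "all statistical analyses will be descriptive", and that "Patient numbers will be determined by those completing the PATENT-1 study and willing to enter the PATENT-2 study". Treatment continues until commercial availability (Protocol 4.1). Summaries are planned by former arm (SAP section 6) and for a long list of subgroups (SAP 6.2).

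**The concern.** The main objective is long-term safety, and death and clinical worsening are the weightiest outcomes collected. A proportion of all patients ever treated mixes people followed for very different times. It does not answer what fraction die or worsen by one, two or three years. Two groups with the same underlying risk can show different percentages only because one stayed under observation longer. The SAP recognises this problem and solves it for adverse events, but its remedy does not reach these two outcomes.

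**Working it through.** The plan states no event rate, dropout rate, follow-up length or sample size for these outcomes, so there is no figure to reproduce. All rates below are assumptions, used to show direction and order of size.

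**Model.** Constant event hazard *h*, constant hazard *c* of leaving for reasons unrelated to the outcome, horizon *T* years.

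- Risk at *T* (the Kaplan-Meier target): 1 − exp(−*hT*)
- Expected crude proportion: *h*/(*h*+*c*) × [1 − exp(−(*h*+*c*)*T*)]

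**1. Three-year illustration, assumed risk 25%.** *h* = −ln(0.75)/3 = 0.0959 per year.

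- Net exit probability 30%: *c* = −ln(0.70)/3 = 0.1189. Crude = 0.0959/0.2148 × (1 − 0.75 × 0.70) = 0.446 × 0.475 = 21.2%, which is 3.8 points below 25%.
- Net exit probability 50%: *c* = −ln(0.50)/3 = 0.2310. Crude = 0.0959/0.3269 × (1 − 0.75 × 0.50) = 0.293 × 0.625 = 18.3%, which is 6.7 points below.

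The 30% and 50% are probabilities of leaving in the absence of events. The shares actually leaving event-free are *c*/(*h*+*c*) times the same bracket, about 26% and 44%. Read as two groups with identical risk, these figures differ by 2.9 points through exit alone.

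**2. Range.** With *h* from 0.05 to 0.20 and *c* from 0.02 to 0.20 per year:

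| Horizon | Crude ÷ Kaplan-Meier risk | Largest gap (points) |
|---|---|---|
| 1 year | 0.91 to 0.99 | 1.6 |
| 2 years | 0.83 to 0.98 | 5.4 |
| 5 years | 0.65 to 0.96 | 20.0 |

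**3. Exits for worsening counted as events (SAP 4.3).** With *h* = *c* = 0.10 and *T* = 2, let a share *q* of exits count as events.

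| *q* | Risk | Crude | Gap (points) |
|---|---|---|---|
| 0 | 18.1% | 16.5% | 1.6 |
| 0.5 | 25.9% | 24.7% | 1.2 |
| 1 | 33.0% | 33.0% | 0 |

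This relief applies to the composite only. A withdrawal for worsening is not a death.

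**4. No time horizon.** Assume administrative follow-up uniform over 1 to 5 years, *h* = 0.10 and *c* = 0.05. The whole-study crude proportion is 0.10/0.15 × {1 − [exp(−0.15) − exp(−0.75)]/(0.15 × 4)} = 0.667 × (1 − 0.647) = 23.5%. The risks are 18.1% at 2 years, 25.9% at 3 and 39.3% at 5. The percentage lies above one and below the others, and nothing in it tells the reader which time it describes.

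**The case against.** - **Kaplan-Meier is already planned for clinical worsening.** A reader might infer from SAP 6.2 that the curve was dropped, or from the general rules in SAP 4.1 that event times will simply be averaged. The documents do not support either reading. Protocol 6.1 presents the incidence tables "together with the Kaplan-Meier survival curve", SAP section 6 adopts the protocol's methods, and nothing in SAP 6.2 says that censoring will be ignored. This stands. What is missing is the detail: time points, intervals and a censoring rule.
- **Not every early leaver counts as event-free.** SAP 4.3 treats death and withdrawal due to clinical worsening as events, and starting new PH-specific treatment because of worsening is a component. This stands too. The issue concerns those who leave for other reasons. Withdrawal as such is not among the seven components in SAP 6.2 or in Protocol 4.6.4, so the SAP should say how it enters.
- **Crude figures need not understate risk.** A general claim of understatement goes too far. It holds at a fixed horizon with unrelated exit, whereas a whole-study percentage can fall on either side of the risk at a given time.
- **Some detail lies outside these documents.** The SAP refers to a separate specification of tables and figures, and to a clinical-worsening sensitivity analysis from the supplementary SAP of study 12934. Either may add output. Neither can be checked here, and the SAP should state the main method itself.
- **The study is descriptive.** No test or error rate is affected. True, but a descriptive safety estimate still has to refer to a defined period.
- **Death is partly covered.** Day of death is listed, death is a component of the composite, and adverse events get person-time rates. None of these gives an all-cause mortality estimate over time.

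**Conclusion.** The concern holds in a limited form. The clearest gap is death: an open-ended long-term safety study plans neither a survival estimate nor a person-time rate for it. For clinical worsening, the method exists in the protocol but is under-specified in the SAP, which gives it second place to crude counts.

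The size cannot be fixed from the documents. Under constant hazards and unrelated exit, the fixed-time gap is small at one year (at most 1.6 points in the range tried), about 4 to 7 points in the three-year illustration, and up to 20 points at five years. For the composite it shrinks as more exits count as events. Multi-year follow-up is itself an inference, from the open-ended treatment phase and from protocol versions dated 2008 to 2015 in the SAP; no follow-up figures are given.

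This is worth correcting before the final analysis. It does not invalidate the design.

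**What to change.** **SAP 6.4, death.** Add Kaplan-Meier estimates of all-cause death at fixed times, with confidence intervals and numbers at risk, and deaths per 100 patient-years. Censor at last known contact, and count deaths and person-time over the same window.

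**SAP 6.2, clinical worsening.** Name the protocol's Kaplan-Meier method and give the same fixed-time estimates. Censor at the end of event collection, which Protocol 4.6.4 places at termination of study drug. The flow chart in Protocol 10.1 also marks the event evaluation at the Safety Follow-Up Visit, so the rule should say which applies. Add events per 100 patient-years, state how withdrawal for worsening enters, and keep crude counts by component as supportive.

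**Limitation to state.** Both sets of estimates assume that exit is unrelated to prognosis. That is doubtful, above all for death after withdrawal for worsening, since scheduled follow-up ends about 30 days after the last dose.

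**Cost.** SAP wording and a little standard output. Day of death and duration of study medication are already in the planned output, so no new data collection is needed. Stated risks, especially at longer horizons, are likely to look somewhat less favourable.
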